Mild Intermittent Hypoxia and CPAP: A Multi-Pronged Approach to Treat Sleep
Apnea in Intact and Spinal Cord Injured Humans

Record # 1 R56HL142757-01

Date: November 5th 2018

Experimental Protocol

Specific Aim 1. To determine if IH coupled with CPAP mitigates autonomic, cardiovascular, neurocognitive and metabolic measures both directly and indirectly by improving CPAP compliance as a consequence of LTF of upper airway muscle activity initiated by exposure to IH.

a. Rationale. Many studies have reported that IH directly mitigates co-morbidities typically associated with OSA. In addition, exposure to IH may increase CPAP compliance by initiating LTF of upper airway muscle activity that could enhance upper airway patency leading to a reduction in therapeutic CPAP. Reduced pressures could result in improved compliance and outcome measure.

b. Recruitment. The participants with OSA may be recruited from Sleep Disorders Centers affiliated with Wayne State University and John D. Dingell Veterans Administration Medical Center. The total number of patients studied in these laboratories per year is approximately 4500 and about 40 % of the participants will meet the inclusion criteria. We will also target hypertension clinics at John D. Dingell VA Medical Center and the Detroit Medical Center as additional sites to recruit participants with coincident hypertension and OSA; since up to 30 % of individuals diagnosed with hypertension also have been diagnosed with OSA. Advertisements will also be placed in the local newspaper (i.e. Metro Times) and on various websites (i.e. Craigslist, Facebook and Wayne State University Pipeline). During recently completed studies approximately 100 individuals were screened in order to recruit 20 participants that met the inclusion criteria. In the present proposal we believe this rate of recruitment will improve because our inclusion criteria is less stringent than in the past (i.e. previously we recruited individuals with OSA that fell within a narrow age range and did not suffer from other co-morbid conditions). Based on past experience, once participants meet the inclusion criteria and have successfully completed the screening sleep study and practice trial few drop out beyond this point. Nonetheless we have taken into account that 2 participants from each group (see Participants below) may drop out beyond the point of the screening and practice trials, so an additional 4 participants may be enrolled if required.

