d. Protocol and Measurements. Visit 1: Health, lifestyle and sleep questionnaires (i.e. SF-36 Health survey and Epworth Sleepiness Scale) along with pulmonary function tests, blood pressure measurements, a 12-lead electrocardiogram and a physical examination will be completed. Visit 2: A sleep study beginning at approximately 10 pm will be completed. The study will be used to confirm the presence or absence of OSA. Visit 3: A sleep study will be completed to determine the therapeutic positive airway pressure required to eliminate flow limitation. In addition, the pressure associated with airway collapsibility will be determined (i.e. the critical closing pressure - PC_{CRIT}). Upon awakening participants in Hypoxia group will undergo a trial exposure to IH (two 2-minute episodes of 8% oxygen separated by two-minute normoxic intervals, with an accompanied 2 mmHg increase in carbon dioxide levels) while sham group will be exposed to room air in order to acclimate to the equipment and accompanying sensations. Visit 4: Following the sleep study, participants will be given a blood pressure holter monitor (ABPM-05, Meditech Inc. Framingham, MA) to measure blood pressure and pulse rate at home over a 24-hour period. Data collection will begin at 6 am on a weekend day. Blood pressure values will be obtained every 20 minutes. Participants will be given a diary and an actigraph watch to document activities completed over the 24-hour period. Thereafter data will be standardized relative to activity level (i.e. quiet and active wakefulness and sleep). Participants will be encouraged to adhere to a daily routine that will be replicated following completion of the IH protocol. These measures are being made to monitor the changes in blood pressure associated with activities of daily living. Visits 5 - 19: Following the completion of visits 1-4, participants will visit the lab 15 times over a 3-week period during the day. The participants will visit the laboratory each week day for 3 weeks. If a week day visit is missed it will be replaced by a visit on a week end day. During each visit, participants in Hypoxia group will be exposed to 12 two-minute episodes of 8% oxygen combined with a 2 mmHg increase in carbon dioxide separated by two minute normoxic intervals. The IH protocol will be comprised of a 20-minute baseline period followed by exposure to twelve - two minute episodes of hypoxia [partial pressure of end-tidal oxygen (PETO₂) = 50 mmHg]. Each episode will be interspersed with a 2-minute recovery period under normoxic conditions. The PETCO₂ will be sustained 2 mmHg above baseline values for the last ten minutes of baseline and throughout the remainder of the protocol. In addition to the IH protocol, a group of participants will also be exposed to a sham protocol in addition to being treated with CPAP during sleep. The sham protocol will be administered during wakefulness for a minimum of 15 days over a 3-week period. During the sham protocol the participants will be exposed to atmospheric levels of oxygen and carbon dioxide for the duration of the IH protocol. During the IH and sham protocol respiratory

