Visits 5, 12 & 19: On visits 5, 12 & 19 additional autonomic, cardiovascular, neurocognitive and metabolic measures will be obtained. Upon entering the laboratory participants will complete a series of questionnaires and tasks to assess vigilance and neurocognitive function. The Pathfinder Number Test and Psychomotor Vigilance Task will assess attention and psychomotor function. The Buschke Selective Reminding Test will assess learning and memory. The Epworth Sleepiness Scale will assess day time sleepiness. The Mini Mental State Examination will be used

to assess five areas of cognition function (i.e. orientation, registration attention, calculation, recall and language). Thereafter, 15 ml of blood will be sampled prior to exposure to the IH or sham protocol to identify potential metabolic (i.e. lipid profile, hemoglobin A1C), inflammatory (i.e. asymmetric dimethylarginine and high sensitivity C-reactive protein) and angiogenic/vasculogenic (hypoxia inducible factor 1 α and vascular endothelial growth factor) biomarkers that might reflect the efficacy of exposure to IH. Thereafter, on visits 5 & 19 beat to beat measures of blood pressure will be obtained throughout the IH or sham protocol. Beat to beat measures of blood pressure will also be obtained on visit 12. On visits 12 & 19 daytime exposure to the IH or sham protocol will be followed by a sleep study completed in the laboratory on the evening following the day time visit. Measures obtained during these sleep studies will be similar to the measures described for Visit 3. Visit 20: The protocol outlined for Visit 4 will be repeated on Visit 20.

Data and Statistical Analysis.

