Research staff that will not administer the gases will be assigned to complete a blind analysis of all measures. The staff assigned to analyze data (e.g. ventilation and blood pressure) collected during the direct application of hypoxia might be able to determine the applied stimulus based on the respiratory or cardiovascular response. However, the criteria used to analyze the data is rigorous and bias is unlikely. The Shapiro-Wilk test will be used to test if the data is normally distributed. Assuming that the data will be normally distributed, a two-way analysis of variance with repeated measures in conjunction with Student-Newman Keuls post-hoc test will be used to determine if differences in 24 hour blood pressure measures are evident before and after exposure to IH or the sham protocol. The two factors in the design will “Group (Hypoxia vs. sham)” and “time point (Visit 4 vs. Visit 20).” A similar analysis will be used to determine if primary (i.e. blood pressure, autonomic nervous system activity, therapeutic CPAP, critical closing pressure, limb motor function tests) and secondary (vigilance and neurocognitive measures and blood biomarkers) outcome measures differ before, midway and after completion of the IH or sham protocol. The two factors in the design will be “Group (Hypoxia vs. sham)” and “time point (Visit 5 vs. Visit 12 vs. Visit 19)”. Primary outcome variables collected during IH or the sham protocol (i.e. blood pressure, autonomic nervous system activity, minute ventilation, tidal volume, breathing frequency, PETCO₂, PETO₂) will be analyzed using a three-way analysis of variance with repeated measures in conjunction with Student-Newman Keuls post hoc. The three factors in the design will be “Group (Hypoxia vs. sham)”, “Visit Number (Visit 5 vs. Visit 12 vs. Visit 19)” and “Time Point (Baseline vs. Initial hypoxic episode vs. Final hypoxic episode vs recovery of IH or sham protocol).” A Pearson product-moment correlation and regression analysis will be used to examine the relationship between CPAP adherence (e.g. percentage of days CPAP used over 4 or 6 hours) during the last half of the protocol with changes in the primary and secondary outcome measures for hypoxia and sham groups. If CPAP adherence impacts on the primary and/or secondary outcome measures we expect the slope of the relationship will be greater in Hypoxia group compared to sham group (i.e. for a given level of adherence modification to the primary or secondary outcome variable will be greater in the CPAP and IH group compared to the CPAP and sham group).

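### Haemoglobin A1C is the only glycaemic marker named, and re-measuring it about 9 and 18 days after the first session would heavily understate any glycaemic effect

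*Combined protocol and SAP*

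**What the plan says.** The combined protocol and SAP asks in Specific Aim 1 whether intermittent hypoxia (IH) with CPAP "mitigates autonomic, cardiovascular, neurocognitive and metabolic measures both directly and indirectly".

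The metabolic part is specified in section d, Protocol and Measurements, under Visits 5, 12 & 19: "15 ml of blood will be sampled prior to exposure to the IH or sham protocol to identify potential metabolic (i.e. lipid profile, hemoglobin A1C", followed by inflammatory and angiogenic markers. All are described as "biomarkers that might reflect the efficacy of exposure to IH". Glucose, insulin and glycated serum protein are not mentioned anywhere in the document.

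On timing, the same section says "participants will visit the lab 15 times over a 3-week period during the day" and "The participants will visit the laboratory each week day for 3 weeks", with a missed weekday made up at a weekend. Table 1 marks a blood draw at Visits 5, 12 and 19 only; Visit 20 has automated blood pressure and nothing else.

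Data and Statistical Analysis classes blood biomarkers as secondary. It tests whether "outcome measures differ before, midway and after completion of the IH or sham protocol" with a two-way repeated-measures ANOVA (group by Visit 5, 12, 19). It also relates CPAP adherence in the last half of the protocol to changes in primary and secondary outcomes, and expects a steeper slope in the Hypoxia group.

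**The concern.** A1C reflects glycaemia averaged over the life of the circulating red cells. If that life is several months, most of the A1C value at Visit 12, and still most of it at Visit 19, was laid down before the first session. The marker and the observation window then do not match, and no later draw lets the marker catch up.

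What is at stake is narrow but real. If IH changed glucose, the only glycaemic outcome would show a fraction of that change. The group-by-time comparison would be shrunk towards zero. So would the adherence slopes and the difference between them. An unchanged A1C could not separate no effect from an effect not yet expressed, and the plan neither justifies A1C over three weeks nor says how an unchanged value will be read.

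**Working it through.** The plan gives no effect size, SD, power or A1C kinetics, so there is no stated figure to reproduce.

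**1. Timing.** Inputs: 15 consecutive weekday visits (Visits 5-19), with blood taken before that day's session. Visit 12 is the 8th of these visits and Visit 19 the 15th, so the draws follow 7 and 14 sessions. Counting calendar days from Visit 5, before any weekend make-up visits:

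| Weekday of Visit 5 | Days to Visit 12 | Days to Visit 19 |
|---|---|---|
| Monday | 9 | 18 |
| Tuesday, Wednesday | 9 | 20 |
| Thursday, Friday | 11 | 20 |

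**2. Share of the eventual A1C change expressed.** Assumptions, not from the documents: red-cell life L of 90-120 days, cell ages spread evenly from 0 to L, glycation proportional to accumulated glucose exposure, and an immediate, sustained shift in mean glucose at Visit 5. The share after d days is 1 - (1 - d/L)².

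| L | Day 9 | Day 11 | Day 18 | Day 20 |
|---|---|---|---|---|
| 120 days | 1 - 0.925² = 14.4% | 17.5% | 1 - 0.85² = 27.8% | 30.6% |
| 90 days | 1 - 0.90² = 19.0% | 23.0% | 1 - 0.80² = 36.0% | 39.5% |

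A shorter life of 80 days gives 21.2% at day 9 and 39.9% at day 18. To reach 50% at day 18, L would have to be 18/(1 - √0.5), about 61 days.

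**3. Gradual onset.** If the glucose shift builds linearly from zero to full size over 18 days, the share is (2/(18L)) × (d²/2 - d³/(6L)):

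- L = 120: 3.7% at day 9 and 14.3% at day 18.
- L = 90: (2/1620) × (40.5 - 1.35) = 4.8% at day 9 and (2/1620) × (162 - 10.8) = 18.7% at day 18.

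**4. Adherence correlation.** A glucose change produced by CPAP use in the last half of the protocol has about 9 days to reach the Visit 19 value. From step 2, that is 14-19% expressed. Slopes in both groups shrink by that factor, and so does their difference.

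**5. Alternative marker.** Assumption, not from the documents: a glycated serum protein follows a sustained shift as 1 - 2^(-d/h), with half-life h of 14-20 days. Day 9: 27% (h = 20) to 36% (h = 14). Day 18: 46% to 59%. At day 18 this is between 46.4/36.0 = 1.3 and 59.0/27.8 = 2.1 times the A1C share.

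**6. Power with 4 per group.** Assumptions: t-test on between-group change, two-sided 5% level. An 80% chance of detection needs a difference of 2.38 SD of the change. If 2.38 SD is the eventual difference and only 28-36% is expressed, power is about 12-18%. The eventual difference needed for 80% power is then 2.38/0.36 = 6.6 to 2.38/0.278 = 8.6 SD for A1C, against 2.38/0.59 = 4.0 to 2.38/0.46 = 5.2 SD for the glycated protein, each in its own marker's SD units. A fully expressed difference of 1 SD has about 22% power.

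**The case against.** The strongest reply is that this does not matter at this stage. With 4 per group almost nothing will be detected: the alternative marker still needs an eventual difference of 4.0-5.2 SD, and even a marker without lag has about 22% power at 1 SD. That stands as a statement about power, and changing the assay will not make this trial conclusive on glycaemia. It does not remove the point. Attenuation is separate from noise: the expected A1C difference is about a third of its eventual size at any sample size, and pooling or enlarging the study would not correct it.

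Three stronger readings are tempting, and the documents do not support them.

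- A reader might infer that A1C cannot respond at all in this window. Under the assumptions above, 28-36% of the change is expressed by day 18, so the response is reduced but not absent.
- A reader might infer that a real metabolic effect would be missed. The panel also includes a lipid profile, to which this argument does not apply, so the point is confined to glycaemia.
- A reader might infer that an unchanged A1C will be reported as evidence against Aim 1. No section says so. The biomarkers are described tentatively, as possible indicators of efficacy, and are secondary. What can be said is that the plan gives no rule for reading an unchanged value.

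Two further limits are fair. The list of metabolic markers is introduced by i.e., which this protocol also uses for examples (the recruitment websites, for instance), so A1C is the only glycaemic marker named, not provably the only one intended. And a switch to fasting glucose and insulin would not be free: at these visits the cognitive tests come before the blood draw and the blood pressure recordings follow it, so fasting would change the conditions for the cognitive tests and possibly for a primary outcome.

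**Conclusion.** The point holds for glycaemia. The single named glycaemic marker is re-measured only 9-11 and 18-20 days after the first session and never later. With a Monday start it would carry about 14-19% of its eventual change at Visit 12 and 28-36% at Visit 19; the later calendar days give at most 23% and 40%. Gradual onset lowers this to about 4-5% and 14-19%. These figures rest on an assumed red-cell life of 90-120 days and the simple ageing model above, but the conclusion is not sensitive to them: even half expression at day 18 would need a life of about 61 days.

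An unchanged A1C in this trial would say little about glycaemic effect, and an observed change would understate its long-run size. The consequence is limited to one secondary biomarker and to its part in the adherence analysis. It is a cheap improvement to make; it does not threaten the trial's main conclusions.

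**What to change.** From the existing 15 ml draws at Visits 5, 12 and 19, measure fructosamine or glycated albumin and name it as the glycaemic outcome in both the ANOVA and the adherence analysis. Neither needs fasting. Keep A1C at Visit 5 as a baseline descriptor. Add one sentence to Data and Statistical Analysis: a change, or lack of change, in A1C over about 18 days will not be taken as evidence for or against a glycaemic effect.

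For the 8 planned participants this means 24 low-cost assays added (8 × 3) and 16 A1C assays dropped (8 × 2), with no extra visit or draw. The protocol does not describe tube types or spare volume, so the sponsor should confirm that the 15 ml is enough. The other costs are a marker less familiar to readers and a response that is still incomplete at day 18 (46-59% under the assumed half-life). Fasting glucose and insulin avoid the red-cell lag, but should be used only if the sponsor is satisfied that fasting is compatible with the cognitive and blood pressure measures taken at the same visits. If no assay can be added, the interpretive sentence alone is worth including.

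### Blind analysis is promised for all measures, but session recordings at Visits 5, 12 and 19 probably reveal the arm, and no masking is described for the blood pressure and autonomic outcomes taken from them

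*Combined protocol and SAP*

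**What the plan says.** Data and Statistical Analysis opens with a general promise: "Research staff that will not administer the gases will be assigned to complete a blind analysis of all measures". It then makes an exception in substance. Staff who analyse data collected while hypoxia is being applied, with ventilation and blood pressure given as examples, "might be able to determine the applied stimulus based on the respiratory or cardiovascular response". The answer to that exception is one sentence: "However, the criteria used to analyze the data is rigorous and bias is unlikely". Neither the criteria nor any masking step is described there or elsewhere.

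The same section lists what is taken from the sessions: "Primary outcome variables collected during IH or the sham protocol (i.e. blood pressure, autonomic nervous system activity, minute ventilation", followed by further respiratory variables that include end-tidal CO2 and end-tidal oxygen. The time-point factor of the three-way model is "Baseline vs. Initial hypoxic episode vs. Final hypoxic episode vs recovery of IH or sham protocol", so resting and exposure segments of one session enter one analysis. A separate two-way analysis asks whether primary and secondary "outcome measures differ before, midway and after completion of the IH or sham protocol", using Visits 5, 12 and 19. Blood pressure and autonomic activity are on its primary list.

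The text on Visits 5, 12 and 19 says that on Visits 5 and 19 "beat to beat measures of blood pressure will be obtained throughout the IH or sham protocol", and adds that beat-to-beat pressure is also obtained on Visit 12. Section d, Protocol and Measurements, describes the Hypoxia session as a 20-minute baseline "followed by exposure to twelve - two minute episodes of hypoxia". CO2 is raised from the middle of baseline onward. The sham session uses atmospheric gas throughout.

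**The concern.** The plan states a safeguard, admits that it may fail for part of the data, and replaces it with an assurance that cannot be checked. The admission is framed narrowly, as data collected during hypoxia. The resting segments that give baseline and recovery blood pressure and autonomic values come from the same sessions, so the weakness may reach outcomes that the plan labels primary.

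If an analyst can infer the arm, any judgement in choosing segments or rejecting artefact is made with knowledge of the hoped-for result. Potential Problems & Solutions states that result: lower sympathetic activity and lower blood pressure with intermittent hypoxia plus CPAP. A systematic scoring difference between arms is not removed by averaging, and it passes in full into the estimated difference. An unqualified description of the analysis as blind would also claim more than the procedures support.

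**Working it through.** The plan gives no figure for this point, and no alpha, effect size or SD. The check is therefore a comparison of the text, a timeline, and one calculation on assumed values.

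**1. Can the arm be inferred from a session recording?** Section d gives 20 minutes of baseline, then 12 episodes of 2 minutes, each with a 2-minute recovery period.

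- Length to the end of the episodes: 20 + 12 × (2 + 2) = 68 minutes, or 66 if only 11 recovery intervals are counted. The length of end recovery is not given.
- In the Hypoxia arm, end-tidal CO2 is held 2 mmHg above baseline from minute 10 onward, and end-tidal oxygen is taken to 50 mmHg in each episode. The sham arm has neither.
- Time with an arm-specific gas target: 68 − 10 = 58 minutes, and 58/68 = 85%. On the shorter count, 56/66 = 85%.
- Time that is the same in both arms by design: the first 10 minutes of baseline (10/68 = 15%).

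Ventilation, end-tidal CO2, end-tidal oxygen and saturation are monitored continuously, and both end-tidal gases are themselves analysed. A person with the full recording could very likely infer the arm. The plan's wording, that staff might be able to, understates this.

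**2. Which outcomes are exposed?**

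| Outcome | Source | Exposed? |
|---|---|---|
| Session blood pressure and autonomic activity during episodes | Visits 5, 12, 19 | Yes; conceded in the plan as a possibility |
| Session blood pressure and autonomic activity at baseline and recovery | Same sessions | By inference; no safeguard described |
| 24-hour blood pressure | Ambulatory monitor, Visits 4 and 20 | Only through staff overlap |
| Blood biomarkers and cognitive tests | Visits 5, 12, 19, before exposure | Only through staff overlap |
| Therapeutic CPAP and critical closing pressure | Sleep studies, Visits 3, 12, 19 | Only through staff overlap |

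The documents do not say whether staff overlap. The one check on unblinding, in item (v) of Potential Problems & Solutions, concerns what participants know, not what analysts know.

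**3. What could a scoring shift do?** This is hypothetical. The documents supply only n = 4 per arm (section c, Participants). Assumed here: a two-sided 5% level, a two-sample t test on the change (6 degrees of freedom, critical value 2.447), an SD of change of 5 or 8 mmHg, no true effect, and a systematic shift b in the between-arm change.

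Noncentrality = b / (SD × √(2/4)). The denominator is 3.54 mmHg for SD 5 and 5.66 mmHg for SD 8.

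| Shift b | SD 5: noncentrality, rejection rate | SD 8: noncentrality, rejection rate |
|---|---|---|
| 1 mmHg | 0.28, 5.7% | 0.18, 5.3% |
| 2 mmHg | 0.57, 7.7% | 0.35, 6.0% |
| 4 mmHg | 1.13, 16.0% | 0.71, 9.2% |

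The estimate is off by b whatever the SD. The t test is a simple stand-in for the planned repeated-measures analyses of variance, so the rates show scale only.

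**The case against.** The strongest reply is that the plan discloses the limitation itself, words it as a possibility, and confines it to data collected during hypoxia. It does not say that one person scores all segments, that pressure is scored with the gas channels on screen, or that beats are picked by hand. The reference to staff assigned to hypoxia-period data is compatible with other staff handling the rest. Extraction may be largely automated. The 24-hour pressures, which are the first blood pressure comparison in the analysis section, lie outside the sessions. A scoring shift of 1 mmHg would hardly move the error rate.

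All of this stands as a limit on the claim. A reader might infer that resting pressures are in fact scored by analysts who can see the allocation, or that the plan admits as much. The documents support neither: they show an opportunity and no safeguard, not a known workflow. A reader might also infer that closing pressure, therapeutic CPAP and the 24-hour pressures are compromised. That would require the same staff to carry knowledge of the arm across, on which the plan is silent.

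The reply does not supply the missing procedure. If scoring is split between staff, masked or automated, the plan does not say so. Disclosing a weakness and then calling bias unlikely on unstated criteria does not make the analysis blind.

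**Conclusion.** The concern holds in a limited form. Baseline and recovery blood pressure and autonomic outcomes from Visits 5, 12 and 19 may be scored by analysts who can infer the arm, and the plan describes nothing to prevent it. The extension from hypoxic to resting segments is an inference. It rests on the shared session, the continuously recorded gas channels and the CO2 rise in late baseline. Other outcomes are affected only through staff overlap.

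The size of any bias cannot be derived from the documents. Under the assumptions shown, the false-positive rate runs from 5.3%, practically nominal, to 16.0%. The upper figure needs a 4 mmHg systematic shift, for which the documents offer no basis, so neither end should be read as an expected value. The change is worth making because it is cheap and would give the claim of blind analysis a defined scope.

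**What to change.** Replace the assurance that bias is unlikely with a procedure in Data and Statistical Analysis:

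1. Staff who administer the gases, and so already know the arm, export the baseline and end-recovery blood pressure and EKG segments of Visits 5, 12 and 19. The exports omit end-tidal oxygen, end-tidal CO2, saturation and ventilation. They carry random codes that are not linked across visits or to any other data.
2. For the baseline outcome compared across visits, use the first 10 minutes of baseline, before CO2 is raised in the Hypoxia arm. Score late baseline and recovery separately, as possibly unblinding: removing the gas channels does not remove a cardiovascular response to the gas.
3. Score and lock the masked segments and all non-session outcomes before anyone who scores them opens the exposure segments.
4. Extract the exposure segments last, with a fixed script or artefact rules stated in advance. Report exposure-period, late-baseline and recovery results as not reliably blinded.

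The cost is a few hours of file handling by existing staff, a later start to the session analysis, and a baseline window of 10 minutes instead of 20. No visit, participant or study procedure changes.

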
(ventilation, PETCO₂, PETO₂, oxygen saturation) and cardiovascular (heart rate and EKG) parameters will be monitored continuously throughout each visit. Likewise, with the exception of visits 5, 12 and 19 (see immediately below) automated and auscultatory blood pressure measurements will be obtained prior to the onset of the protocol, during hypoxic episodes 1, 6 and 12, during recovery from these episodes, as well as, at the midpoint and completion of the end recovery period of the IH or sham protocol. On each day of the protocol participants will continue to be treated with CPAP each night while they sleep in their home environment with the exception of visits 12 and 19 (see Table 1 below). They will be instructed to use CPAP each night for as long as possible.

| | Consent & Screening | Diagnostic Sleep Study | CPAP Titration & PCRT | IH or Sham | Blood Draw | Beat to Beat Blood Pressure | Automated Blood Pressure | Neurocognitive Testing |
|----------|---------------------|------------------------|-----------------------|------------|------------|-----------------------------|--------------------------|------------------------|
| Visit 1 | ✓ | | | | | | ✓ | |
| Visit 2 | | ✓ | | | | | ✓ | |
| Visit 3 | | | ✓ | | | | ✓ | |
| Visit 4 | | | | | | | ✓ | |
| Visit 5 | | | | ✓ | ✓ | ✓ | ✓ | ✓ |
| Visit 6 | | | | ✓ | | | ✓ | |
| Visit 7 | | | | ✓ | | | ✓ | |
| Visit 8 | | | | ✓ | | | ✓ | |
| Visit 9 | | | | ✓ | | | ✓ | |
| Visit 10 | | | | ✓ | | | ✓ | |
| Visit 11 | | | | ✓ | | | ✓ | |
| Visit 12 | | | ✓ | ✓ | ✓ | ✓ | ✓ | ✓ |
| Visit 13 | | | | ✓ | | | ✓ | |
| Visit 14 | | | | ✓ | | | ✓ | |
| Visit 15 | | | | ✓ | | | ✓ | |
| Visit 16 | | | | ✓ | | | ✓ | |
| Visit 17 | | | | ✓ | | | ✓ | |
| Visit 18 | | | | ✓ | | | ✓ | |
| Visit 19 | | | ✓ | ✓ | ✓ | ✓ | ✓ | ✓ |
| Visit 20 | | | | | | | ✓ | |

Table 1. Planned measures for each visit to the laboratory (Aim 1). CPAP – continuous positive airway pressure; IH – intermittent hypoxia; PCRT – critical closing pressure

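### Two primary outcomes, therapeutic CPAP and critical closing pressure, are analysed from Visit 5, but the schedule measures them at Visits 3, 12 and 19

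*Combined protocol and SAP*

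**What the plan says.** The Data and Statistical Analysis section puts therapeutic CPAP and critical closing pressure in its list of primary outcomes. It assigns the whole list, with the secondary outcomes, a repeated-measures analysis of variance comparing values before, during and after the protocol. The factors are group and "time point (Visit 5 vs. Visit 12 vs. Visit 19". The same section gives 24-hour blood pressure its own pair of visits, 4 and 20.

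The measurement schedule is set out in Protocol and Measurements (section d) and Table 1:

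- **Visit 3, therapeutic pressure:** "Visit 3: A sleep study will be completed to determine the therapeutic positive airway pressure required to eliminate flow limitation".
- **Visit 3, critical closing pressure:** in the same study, "the pressure associated with airway collapsibility will be determined".
- **Visit 3, order of events:** the practice exposure comes after that study: "Upon awakening participants in Hypoxia group will undergo a trial exposure to IH".
- **Home nights:** during the protocol, participants use CPAP "each night while they sleep in their home environment with the exception of visits 12 and 19".
- **Later sleep studies:** "On visits 12 & 19 daytime exposure to the IH or sham protocol will be followed by a sleep study", and "Measures obtained during these sleep studies will be similar to the measures described for Visit 3".
- **Table 1:** the titration and critical closing pressure column is ticked at Visits 3, 12 and 19 only.

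One passage differs. Potential Problems & Solutions, item (iv), lists sleep instrumentation at Visits 3, 5, 12 and 19.

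**The concern.** The analysis names a starting visit at which, on the schedule, neither outcome is measured, and omits the visit at which both are. An analyst who follows the text finds an empty first level and no instruction on what replaces it.

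The baseline of these two outcomes matters in three places:

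- The Aim 1 rationale is that better upper airway patency lowers the therapeutic pressure, which in turn improves compliance. Showing this needs a value from before exposure.
- The adherence regression uses changes in the primary and secondary outcomes, so it needs a starting value for each.
- Potential Problems & Solutions, item (v), uses improvement in critical closing pressure to judge whether knowledge of the gas mixture influenced the results. Improvement has to be measured from a stated visit.

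**Working it through.** **Inputs.** Four participants per group, 8 in total (section c). Three time levels (Data and Statistical Analysis). Scheduled visits from Table 1. Fifteen sessions, Visits 5 to 19, of 12 episodes each, and a two-episode practice exposure at Visit 3 (section d). Dropout is taken as zero. The plan gives no figure of its own to reproduce here.

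**Step 1: compare the visits.** Analysis levels are {5, 12, 19}. Scheduled measurements are {3, 12, 19}. The overlap is {12, 19}.

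**Step 2: count what the model would contain.** Planned observations per outcome are 8 × 3 = 24.

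| | Levels 5, 12, 19 (as written) | Levels 3, 12, 19 (as scheduled) |
|---|---|---|
| Observations | 0 + 8 + 8 = 16 of 24 | 8 + 8 + 8 = 24 of 24 |
| Group × Time cells with data | 2 × 2 = 4 of 6 | 2 × 3 = 6 of 6 |
| Participants with all three levels | 0 of 8 | 8 of 8 |

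**Step 3: degrees of freedom for Group × Time.** With g groups, t levels and N participants, these are (g − 1)(t − 1) and (N − g)(t − 1).

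- Visits 3, 12 and 19: (2 − 1)(3 − 1) = 2 and (8 − 2)(3 − 1) = 12.
- As written, with the empty level dropped: (2 − 1)(2 − 1) = 1 and (8 − 2)(2 − 1) = 6. The remaining contrast is Visit 12 against Visit 19, both after sessions have begun.

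**Step 4: suppose item (iv) is right and a Visit 5 sleep study exists.** The item does not say whether it would come before or after that day's session.

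- Night after the session, as at Visits 12 and 19: a Hypoxia participant would already have had 1 of 15 sessions, or 12 of 15 × 12 = 180 episodes (6.7%). With the Visit 3 practice exposure that is 12 + 2 = 14 episodes.
- Night before the session: 0 of 15 sessions, but the 2 practice episodes would already have taken place.
- Visit 3 sleep study: no sessions and no practice episodes.

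Visit 3 is thus the only study before any exposure, whichever text about Visit 5 is correct.

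**Step 5: outcomes for which Visit 5 works.** At Visit 5, "15 ml of blood will be sampled prior to exposure to the IH or sham protocol". The blood biomarkers therefore have a value before the first full session, though after the practice exposure. Table 1 also ticks beat-to-beat blood pressure and neurocognitive testing at Visit 5. The mismatch is confined to the two sleep-study outcomes.

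**The case against.** The best reply is that this is a labelling slip. The section says in words that it wants a comparison starting before the protocol, and on the Table 1 schedule only one titration study precedes the sessions. One time factor was written for a pooled list that also contains limb motor function tests, which appear nowhere in Table 1 or the visit descriptions. The list was evidently not written outcome by outcome, and Visit 5 may be shorthand for the starting value. On that reading any analyst would use Visit 3. The counts in the working all express one fact, an empty level, and do not measure bias or error rate.

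Much of this stands. On the Table 1 schedule there is little real freedom in choosing the baseline, and the check in item (v) is informal. But the text does not say that Visit 5 is shorthand, and the same section does tailor the visits for 24-hour blood pressure. Item (iv) lists Visit 5 in addition to Visit 3, so it is not a simple exchange of one number for the other. If it is correct, there are two early values to choose between.

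A second reply is that the contradiction should be settled before a baseline is named. It must be settled, but Visit 3 precedes all exposure either way, so naming it does not prejudge the answer.

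**Conclusion.** The concern holds. Followed literally on the Table 1 schedule, the stated analysis leaves two primary outcomes with no pre-exposure level: 0 of 8 observations at Visit 5, 16 of 24 overall, and 4 of 6 Group × Time cells. It also excludes the Visit 3 measurement. These counts assume 4 participants per group, no dropout, and Table 1 taken as the schedule. If item (iv) is the correct text, Visit 5 has data, but Table 1 and the visit descriptions then omit a sleep study and the starting value still has to be named. The documents need reconciling on either reading. This should be fixed, but it is a defect of specification: no data are lost and outcomes actually measured at Visit 5 are unaffected.

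**What to change.** 1. In Data and Statistical Analysis, give therapeutic CPAP and critical closing pressure their own time factor: Visit 3 vs Visit 12 vs Visit 19.
2. Name Visit 3 as their baseline wherever a change is used, including the adherence regression and the item (v) check.
3. Keep Visit 5 vs Visit 12 vs Visit 19 for outcomes taken at those visits.
4. Reconcile Potential Problems & Solutions, item (iv), with Table 1 and the visit descriptions by stating whether any sleep study is planned at Visit 5. If one is intended on the night after that session, say that it follows the first full session and is not the pre-exposure baseline.

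The cost is a few lines of text. Visit 3 is already scheduled, so the change of baseline needs no new visit, procedure or participant.
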